XVI. STATISTICAL METHOD

PILOT step

During this stage, patients will not be randomized and will all receive sunitinib. After a total of 10 chemoembolization sessions, inclusions will be discontinued and tolerance results will be reviewed by a committee of independent experts.

Patients included in this pilot phase will be particularly monitored for the purpose of detecting two potential complications associated with the combination of sunitinib- chemoembolization: severe bleeding and liver failure. The observed rate of bleeding or liver failure after chemoembolization is in the order of 10 to 15% in recent studies . One or two toxicities are expected among the 10 chemoembolization sessions. If 4 or more toxicities occur, then the toxicity of the sunitinib-chemoembolization combination is considered unacceptable and the trial is discontinued. If 3 or fewer toxicities occur, the toxicity is considered acceptable and the trial is continued in phase II with randomization. Patients included in the pilot phase will not be included in the final analysis of the SATURN trial.

The results of the pilot phase will be sent to AFFSAPS for information.

Phase II step

Patients included during this first step will be specially monitored for the detection of two complications: severe bleeding and liver failure (as defined above) in the sunitinib arm. The expected rate of severe haemorrhage and/or liver failure in patients undergoing TACE is approximately 10 % to 15%, as observed in recent studies with a TACE alone arm (25). We defined the unacceptable toxicity rate as 30 % in patients undergoing TACE plus sunitinib treatment.

Using Fleming one step design with the following hypotheses:

H0: An occurrence rate of bleeding or liver failure 1 week after last administration of the TACE-sunitinib combination of 30 % is unacceptable

H1: An occurrence rate of bleeding or liver failure 1 week after last administration of the TACE-sunitinib combination of 15% is expected

It would be required to include 35 patients in each arm.

Among the 35 patients in the Sunitinib arm:

If we observed 8 or more than 8 patients (22.9 %) with severe bleeding or liver failure 1 week after last administration of the TACE-sunitinib, the toxicity rate is not statistically different from 30%. This treatment would be declared unacceptable and inclusions will not be pursued for phase III trial.

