If we observed 7 or less than 7 patients (20 %) with severe bleeding or liver failure 1 week after last administration of the TACE-sunitinib, the toxicity rate is statistically different from 30 %. This treatment would be declared promising and inclusion will be pursued for phase III,

Calculated power is 85.6% and alpha type one error is 13.3 %

Decision rules for phase III trial continuation:

Despite randomization and inclusion of 35 patient in the TACE alone arm we will not use Fleming decision rules for TACE alone arm to pursue randomization since this is the standard arm in the phase III trial.

1. We observed 7 or less than 7 patients (20%) with severe bleeding or liver failure 1 week after last administration of the TACE-sunitinib

We will pursue randomization whatever occurrence of these toxicities in the TACE alone arm since this is the standard arm in the phase III trial.

2. We observe 8 or more than 8 patients (22.9 %) with severe bleeding or liver failure 1 week after last administration of the TACE-sunitinib.

We will check amongst the 35 patients receiving TACE alone:

- If we observed also 8 or more than 8 patients (22.9 %) with severe bleeding or liver failure 1 week after last administration of the TACE alone. Then we will ask an independent data monitoring committee (IDMC) about the opportunity to pursue randomization for phase III trials since these results could reflect the “noise” of TACE toxicities alone.

- If we observed

also 7 or less

than 7 patients (20%) with severe bleeding or liver failure 1 week after last administration of the TACE alone. Then we will ask an independent data monitoring committee (IDMC) about the opportunity to stop randomization for phase III trials.

These 70 patients will be theoretically recruited in 9 months (7.5 pts/ month) and at least 1 week follow-up after last administration of the TACE-sunitinib combination is required then Phase II step will be analyses about 9 months and 1 week after the inclusion of the first patient.

Phase III step

As primary end-point of the phase III study, we have chosen the overall survival for the following reasons:

- The overall survival is generally the primary end-point of trials assessing TACE.

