5.6.2 Phase II

At the end of the 35 patients/arm inclusions of the phase II:

- if the number of patients with severe toxicity (liver failure, bleeding) in the sunitinib arm is less than or equal to 7, the trial will be continued in phase III;
- if the number of patients with severe toxicity (liver failure, bleeding) in the sunitinib arm is greater than or equal to 8, the number of complications (liver failure, bleeding) in the placebo arm should also be considered:
 - if the complication rate (liver failure, bleeding) in the placebo arm is greater than or equal to 8, an independent committee of experts will have to judge the appropriateness of continuing the trial in phase III since the toxicity in the sunitinib arm may be related to the "background noise" of the toxicity of chemoembolization alone;
 - if the complication rate (liver failure, bleeding) in the placebo arm is less than or equal to 7, the independent expert committee will have to judge whether to stop the trial.

The decision rules will apply only to the sunitinib/chimio/embolization arm; the placebo/chimio/embolization arm will be maintained in all cases for la phase III, if it occurs, with this arm serving as the control arm.

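### For 8 or more affected sunitinib patients the protocol both stops before phase III and refers the result to a committee; the stated 13.3% error fits only a binding stop

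*Protocol*

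**What the plan says.** Protocol section XVI, Phase II step, sets up a single-arm test of the sunitinib arm ("Using Fleming one step design with the following hypotheses"). The unacceptable rate is 30% and the expected rate 15%, with 35 patients per arm. Seven or fewer affected patients leads to phase III. For 8 or more it says: "This treatment would be declared unacceptable and inclusions will not be pursued for phase III trial". No exception and no committee is mentioned. The operating characteristics follow: "Calculated power is 85.6% and alpha type one error is 13.3" per cent.

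Under the sub-heading on decision rules for phase III continuation, the same section treats 8 or more differently. The TACE-alone count is examined. If it is also 8 or more: "Then we will ask an independent data monitoring committee (IDMC) about the opportunity to pursue randomization for phase III trials". If it is 7 or fewer, the committee is asked about stopping.

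SAP 5.6.2 keeps only the committee version. When placebo has 8 or more, the committee judges whether continuing is appropriate; when placebo has 7 or fewer, "the independent expert committee will have to judge whether to stop the trial". SAP 5.5.2 still gives the 13.3% risk for a one-step Fleming design. Neither document gives the committee a criterion or states an error rate for the committee rule.

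**The concern.** One observed result leads to two different actions. Under the first statement the trial ends before phase III. Under the second, and under the SAP, neither placebo branch stops automatically.

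This affects how the error rate is read. In this design a type I error means going on to phase III when the true toxicity rate on sunitinib is 30%. If some results of 8 or more can still lead to phase III, the chance of that error is no longer the chance of seeing 7 or fewer. The rule is the safety check before the remaining 120 patients (190 − 70) are enrolled, so a sponsor, ethics committee or monitoring committee reading 13.3% should know which rule it describes.

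**Working it through.** **Inputs**
- Patients per arm, n = 35: "It would be required to include 35 patients in each arm" (protocol XVI).
- Null rate 30%: "We defined the unacceptable toxicity rate as 30 % in patients undergoing TACE plus sunitinib treatment" (protocol XVI).
- Alternative rate 15%: "H1: An occurrence rate of bleeding or liver failure 1 week after last administration of the TACE-sunitinib combination of 15% is expected" (protocol XVI).
- Continue at 7 or fewer (protocol XVI; SAP 5.6.2).
- Expected rate with TACE alone: about 10% to 15% (protocol XVI).
- Not in the documents: the probability *c* that the committee continues once consulted, and any TACE-alone rate above 15%. Both are treated as assumptions.

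**Step 1: reproduce the plan's figures.** Let X be the number affected in the sunitinib arm, binomial with n = 35.
- Alpha = P(X ≤ 7 | 0.30) = 0.1326, stated as 13.3%.
- Power = P(X ≤ 7 | 0.15) = 0.8562, stated as 85.6%.

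Both match. They belong to the rule of continuing if and only if X ≤ 7. Alpha here is a single lower tail, although SAP 5.5.2 calls the risk two-sided.

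**Step 2: the committee rule, with continuation possible only when placebo is also 8 or more.** Let Y be the number affected in the placebo arm, independent of X. Then

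P(continue) = P(X ≤ 7) + P(X ≥ 8) × P(Y ≥ 8) × c.

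At a true sunitinib rate of 30% this is 0.1326 + 0.8674 × P(Y ≥ 8) × c:

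| Placebo rate | P(Y ≥ 8) | c = 0 | c = 0.5 | c = 1 |
|---|---|---|---|---|
| 10% (protocol range) | 0.0200 | 13.3% | 14.1% | 15.0% |
| 15% (protocol range) | 0.1438 | 13.3% | 19.5% | 25.7% |
| 20% (assumed) | 0.4007 | 13.3% | 30.6% | 48.0% |
| 30% (assumed) | 0.8674 | 13.3% | 50.9% | 88.5% |

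For example, at 15% with c = 1: 0.1326 + 0.8674 × 0.1438 = 0.257.

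**Step 3: continuation possible in both branches.** If the committee may also continue when Y ≤ 7, the placebo count no longer limits the result: P(continue) = 0.1326 + 0.8674 × c, for a common c. This is 56.6% at c = 0.5 and 100% at c = 1. Nothing in either document excludes it.

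**Step 4: the effect on power.** At a true sunitinib rate of 15% with c = 1 and the step 2 rule, the chance of continuing is 0.8562 + 0.1438 × 0.0200 = 85.9% (placebo 10%), or 0.8562 + 0.1438 × 0.1438 = 87.7% (placebo 15%). Referral therefore raises the chance of continuing under both hypotheses, and 85.6% is also a minimum.

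**The case against.** The best defence is that the two passages do different jobs. The first reports the outcome of the Fleming test, with its error and power beside it. The actions then come under their own sub-heading, and the SAP carries only those. On this reading the operational rule is identifiable, 13.3% is exact for the test it accompanies, and asking an independent committee to review a crossed toxicity boundary in a randomised trial is a legitimate choice. SAP 5.6.4 also suspends inclusions between the phases until the phase II results are analysed, so the review would come before further enrolment.

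Much of this stands. The SAP does contain a single rule, the arithmetic is right, and a committee is not a fault. The defence fails at one point: the protocol's first statement joins the declaration of unacceptability to the decision not to enrol for phase III, so it is an action as well as a test result. No text says that the later paragraph overrides it. If the later paragraph does govern, 13.3% is not the chance of wrongly continuing, and SAP 5.5.2 does not say so.

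A reader might infer that the real error is 26% to 89%. The documents do not support that. It leaves out the protocol's own lower TACE-alone rate of 10%, uses rates of 20% and 30% that the documents never give for TACE alone, and counts every referral as a continuation. At 30% in both arms sunitinib adds no toxicity, which is the background-noise situation that the referral branch was written for.

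**Conclusion.** The contradiction is real and should be removed. The stated 13.3% and 85.6% are correct for a binding stop at 8 or more. Under the committee rule they are the minimum chances of continuing at true sunitinib rates of 30% and 15%.

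Over the protocol's expected TACE-alone range, with independent arms and continuation only when placebo is also 8 or more, the chance of entering phase III at a true 30% rate runs from 13.3% if the committee always stops to 15.0% (placebo 10%) or 25.7% (placebo 15%) if it always continues. Higher placebo rates are assumptions. If continuation is open in both branches, the only limit is 100%.

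The size of any inflation therefore depends on the true placebo rate and on how the committee decides, and the documents fix neither. They do not show that the error will be inflated: a committee that always stops leaves it at 13.3%.

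**What to change.** Reconcile the two statements in protocol XVI with SAP 5.6.2 so that one action follows from 8 or more affected patients in the sunitinib arm. Which action that should be is for the sponsor to decide. Then:

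- If the stop is binding, keep 13.3% and 85.6% and align the decision rules and SAP 5.6.2 with it.
- If referral is kept, state in protocol XVI and SAP 5.5.2 that 13.3% and 85.6% apply to the single-arm Fleming test only and are the minimum chances of continuing. Give the range from 13.3% to 15.0% (placebo 10%) or 25.7% (placebo 15%), with the committee and placebo-rate assumptions stated. Say whether the committee may continue when placebo has 7 or fewer; if it may, this range does not apply and the text should say so.

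The cost is a few sentences in each document, with no change to sample size or data collection. The stated error becomes less favourable only if referral is kept.

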- The relapse-free survival has been recently recommended for trials performed in an adjuvant setting in patients treated for HCC (26). Yet, TACE is not a curative approach in most cases. Moreover, after TACE, it is frequently difficult to accurately define when an HCC is relapsing, and commonly used criteria (e.g. RECIST criteria) are probably not appropriate enough.
- Management of patients with HCC requires a global approach in order to control the tumour progression, but also the underlying cirrhosis. After TACE, a significant part of the patients will not die from the cancer, but from a complication of the cirrhosis. Only the overall survival takes into account both parameters. If an investigational anticancer drug administered after TACE has an objective effect regarding the tumour growth, but is accompanied by a worsening in the cirrhosis outcome, its global contribution will be relative.

In recent studies assessing TACE, the median overall survival was approximately 60%, but these studies mainly included selected patients, especially with post-viral cirrhosis (1, 2, 25, 27). In France, the main cause of cirrhosis is alcohol. In a recent phase III trial conducted by the FFCD group, tamoxifen alone was compared to tamoxifen plus TACE (28). The cause of cirrhosis was alcohol in 73 % of the patients allocated to the combined therapy

arm. In this arm, survival rate was 32 %, but 26 % of included patients had a Child-B cirrhosis. In another French randomised study comparing TACE and conservative treatment in patients with Child-A cirrhosis, the survival rate at 2 years was 38 % in the TACE arm (29). Since the present study is also restricted to patients with Child-A cirrhosis, we estimated that the survival rate at 2 years will be 40 % in the TACE plus placebo arm.

Hypothesis : to improve OS rate at 2 years from 40 % vs. 60% for Sunitinib arm, with a 90% power and an alpha type I error (bilateral) of 0.05 it is required to observe 130 events and to include 180 pts during 2 years (+5 % lost of follow-up = 10 pts + 180 = 190 pts).

Based on the inclusion of 70 patients in the phase II study, then it will be required to include 190 – 70 = 120 extra patients for the phase III trial.

The minimum follow-up to observe the required number of deaths for final analysis of phase III trial will be about 36 months after the inclusion of the last included patients for total study duration of 5 years.

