5.3 Randomization and blinding

The study is double-blind for sunitinib or placebo (neither the doctor nor the patient knows which treatment is being given).

Stratification by minimization is performed, starting in la phase II, on:

[figure not shown]
- diameter of the primary tumor (< 5 versus \geq 5 cm)
- the presence of one nodule versus the presence of more than one nodule;
- the investigating center.

When a stratified analysis will be performed, it will be performed only according to the diameter of the main tumor and the number of nodules, according to 4 groups:

[figure not shown]
- diameter < 5 cm and a nodule,
- diameter \geq 5 cm and a nodule,
- diameter < 5 cm and more than one nodule,
- diameter \geq 5 cm and more than one nodule.

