5.5.3 Phase III

The assumptions for calculating the number of subjects needed are:

- H_0 : Overall survival in the sunitinib arm is not different from that in the placebo arm; expected 2-year overall survival in the placebo arm is 40%;
- H_1 : Overall survival in the sunitinib arm is different from that in the placebo arm; a 20% difference at 2 years in favor of sunitinib is expected between the two arms (corresponding to a hazard ratio of 0.56).

With a two-sided 5% risk of first-species error, 130 events will be required to achieve 90% power under the previously stated assumption H_1 . Assuming uniform patient inclusion over 2 years, and allowing for a 3-year follow-up after the last inclusion, the number of patients will be 180. To account for a 5% rate of patient attrition, a total of 190 patients will need to be included.

The 70 patients already included in la phase II will be retained for la Phase III, leaving 120 patients to be included.

An interim analysis of the primary endpoint is planned at death 65. This may provide early evidence of superiority of the sunitinib arm. A method of expenditure of the first kind risk (DeMets, 1994), will be used to calculate the nominal values of "p"; this method will make it possible to adjust these threshold values if the intermediate and final analyses are not carried out exactly at the right numbers of events. The expenditure function chosen is an O'Brien function.

Calculations were performed using the R software and the gsDesign library.

| Analysis | Number of events | Nominal value of p | Power to the analysis under hypothesis |
|------------------|------------------|--------------------|--|
| | | | H1 |
| Inter 1 analysis | 65 | 0.0054 | 0.3156 |
| Final analysis | 130 | 0.0439 | 0.5811 |

These values will be adjusted according to the number of actual events at the time of the analyses.

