8.2.5 Characteristics related to the disease

The following characteristics at inclusion will be described using descriptive statistics (no statistical tests):

- CHILD-PUGH score (5 or 6);
- HCC involvement: unilobar or bilobar;
- number of hepatic nodules;
- diagnostic method: histological or according to the Barcelona criteria;
- Associated cirrhosis: yes or no; if yes, etiology: alcohol, hemochromatosis, HBV, HCV or other (A listing of other etiologies will be edited).

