8.7.2 Overall survival

Overall survival will be compared between the 2 treatment groups (Phase III) or described (Phase II) using the stratified logrank test and using the simple logrank test.

The estimation of treatment-related hazard ratios will be performed using a stratified Cox model (Cox, 1984);

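### The SAP's overall-survival analysis names no liver-function or general-condition covariate, although Child-Pugh score, WHO status and AFP are already collected: a cheap efficiency gain is missed and the protocol's multivariate model is left undefined

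*Protocol*

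**What the plan says.** **Protocol XVI, Phase III step.** Overall survival is chosen because it reflects both the tumour and the underlying liver disease: "After TACE, a significant part of the patients will not die from the cancer, but from a complication of the cirrhosis". The same section uses Child class to read earlier trials. It cites 32% survival where 26% of patients were Child-B and 38% at 2 years in a Child-A trial, and then assumes 40% for the control arm. Later it plans univariate and multivariate Cox hazard ratios without naming a covariate.

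**SAP 5.3.** Minimisation uses main tumour diameter, one versus several nodules, and centre. For a stratified analysis, "it will be performed only according to the diameter of the main tumor and the number of nodules, according to 4 groups".

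**SAP 8.7.2.** In phase III, overall survival is compared by a stratified and a simple log-rank test, neither ranked first. The hazard ratio comes from a stratified Cox model with no covariates listed.

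**SAP 8.2.3 to 8.2.5.** WHO status (0, 1, 2), AFP and Child-Pugh score (5 or 6) are collected at inclusion, for description only.

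**SAP 8.1.6.** The general methods include a linearity check for continuous variables in Cox models, but no survival model in the SAP names a continuous variable.

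**SAP 5.5.3.** "With a two-sided 5% risk of first-species error, 130 events will be required to achieve 90% power".

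**The concern.** The protocol treats liver function as a driver of the primary endpoint, yet no variable describing liver function or general condition enters the SAP's overall-survival analysis. If such variables are prognostic, a model that includes them usually tests the treatment effect with more power at the same number of deaths. Here the data are collected anyway.

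There is also a prespecification gap. The protocol promises a multivariate model, the SAP does not define it, and SAP 8.8 lists no exploratory analyses. Any adjusted model produced later would have its covariates chosen after the fact, possibly with results in view. If the arms then differed by chance in Child-Pugh score, no agreed analysis would take account of it.

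**Working it through.** **1. Reproduce the plan's figures.**
- Effect: the protocol aims "to improve OS rate at 2 years from 40 % vs. 60% for Sunitinib arm". Under exponential survival, HR = ln 0.6 / ln 0.4 = 0.557. The SAP gives "corresponding to a hazard ratio of 0.56".
- Deaths, Freedman: (1.960 + 1.282)² × [(1 + HR)/(1 − HR)]² gives 131 at HR 0.557 and 133 at 0.56, against 130 stated. The Schoenfeld formula gives 124 and 126.
- Power at 130 deaths: 90.0% and 89.5% (Freedman); 91.5% and 91.1% (Schoenfeld).
- Patients: "Assuming uniform patient inclusion over 2 years, and allowing for a 3-year follow-up after the last inclusion", the probability of death by the analysis is 0.834 (control) and 0.636 (sunitinib), mean 0.735. Then 130 / 0.735 = 177, against 180 stated; 180 / 0.95 gives 190.
- The SAP's power table, which includes the interim look, adds up to 0.3156 + 0.5811 = 0.897.

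The stated 90% is therefore reached with no covariate adjustment.

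**2. Simulate the gain from adjustment.** The documents give no prognostic effect or prevalence for the three variables, so all of these are assumptions. Both simulations compare the stratified Cox treatment test (critical value 1.96) without and with covariates. Accrual is uniform over 24 months and analysis is at the 130th death. They are single-look figures and do not include the interim analysis.

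*Simulation A*: 180 patients; 35% Child-Pugh 6; WHO 0/1/2 at 60/30/10%; log AFP standard normal; diameter and nodule HR 1.3 each; marginal 2-year survival 40% vs 60%; 6,000 trials per scenario.

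| Assumed HRs | Without | With | Gain (points) |
|---|---|---|---|
| Child-Pugh 1.3 only | 90.1% | 90.3% | 0.2 |
| Child-Pugh 1.5 only | 90.0% | 90.8% | 0.8 |
| Child-Pugh 2.0 only | 89.8% | 92.0% | 2.2 |
| Child-Pugh 1.5, WHO 1.3 per level, AFP 1.3 per SD | 89.6% | 92.1% | 2.5 |
| Child-Pugh 2.0, WHO 1.4, AFP 1.4 | 88.6% | 94.2% | 5.6 |

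With no treatment effect (12,000 trials), the type I error was 5.1% without and 5.4% with covariates. The Monte Carlo standard error is √(0.05 × 0.95 / 12,000) = 0.2 point.

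*Simulation B*: 190 patients; 30% Child-Pugh 6; 35% WHO 1 or more; AFP as a standard normal score; diameter HR 1.4 and nodule HR 1.3; 3,000 trials per scenario; Monte Carlo error about 0.5 point. HRs are in the order Child-Pugh / WHO / AFP per SD.

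| Assumed HRs | 40% vs 60% held marginally | Implied conditional HR | 0.557 taken as the conditional HR |
|---|---|---|---|
| Weak: 1.3 / 1.2 / 1.15 | 90.4% → 90.3% | 0.547 | 89.3% → 90.6% |
| Moderate: 1.5 / 1.5 / 1.3 | 91.6% → 93.1% | 0.536 | 86.9% → 90.3% |
| Strong: 2.0 / 2.0 / 1.5 | 89.3% → 95.9% | 0.509 | 80.6% → 90.3% |

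The plan derives its hazard ratio from arm-level 2-year survival, so the marginal column matches the documents. It gives gains of −0.1, 1.5 and 6.6 points. The last column is a sensitivity case.

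**3. Chance imbalance.** With 95 per arm and 35% Child-Pugh 6, the SD of the between-arm difference is √(0.35 × 0.65 × 2 / 95) = 0.069, about 7 points. A one-SD imbalance shifts the log HR by about 0.069 × ln 1.5 = 0.028 to 0.069 × ln 2.0 = 0.048. The standard error at 130 deaths is about 2/√130 = 0.175, so the shift is 0.16 to 0.27 standard errors.

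**The case against.** The strongest reply is that a log-rank test and Cox model stratified on two of the three minimisation factors is standard and valid, and already delivers the planned power. That stands. Four further points also stand.

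- *The SAP does not forbid covariates.* SAP 5.3 says which minimisation factors form strata. The protocol's multivariate hazard ratios and the linearity check in SAP 8.1.6 suggest that adjusted models were in mind. What is missing is their content.
- *The contrast within Child-Pugh A is narrow.* At the SAP's bilirubin limit, 15 mg/L × 85.5/50 = 25.7 µmol/L, below the 35 µmol/L at which a second point is scored. Prothrombin activity of at least 50% scores one point except at the boundary. A score of 6 therefore comes almost entirely from albumin, mild ascites or confusion. The only liver-function contrast in the documents is between trial populations, not 5 versus 6, so an HR of 2.0 is not supported. The larger gains need WHO status and AFP, on which the cirrhosis sentence says nothing.
- *Tempting stronger readings fail.* A reader might infer that the trial is underpowered; the figures reproduce, so it is not. A reader might infer that omitting prognostic factors biases the hazard ratio towards 1; the marginal and conditional hazard ratios are different quantities, and the trial was sized on the marginal one. A reader might infer that chance imbalance invalidates the primary result; the test's error rate already covers it, and a typical shift is about a quarter of a standard error or less.
- *Phase III is conditional on the phase II result*, and SAP 7.3 allows changes before database freeze.

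None of this removes the case for naming the covariates. In these simulations adjustment never costs power beyond simulation error.

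**Conclusion.** The point holds as a missed efficiency gain and an undefined model, not as an error. The planned analysis is valid and reaches about 90% power. With 40% vs 60% holding marginally, adjustment for all three covariates adds about 0 to 6.6 points of power. It adds 0.2 to 2.2 points if only Child-Pugh is prognostic and essentially nothing if all effects are weak. Gains above about 3 points need moderate to strong effects, which the documents neither state nor support. The figure of nearly 10 points (80.6% to 90.3%) applies only if 0.557 is read as a covariate-conditional hazard ratio, which is not how the plan derives it. All these sizes rest on assumed prognostic effects and prevalences and on a single-look test.

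**What to change.** Before database freeze, specify in SAP 8.7.2 a Cox model stratified by the four diameter-by-nodule groups, with treatment and three fixed covariates measured at inclusion: Child-Pugh (5 vs 6), WHO status (0, 1, 2) and log AFP.

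Take both the treatment test and the reported hazard ratio from this model. Changing only the hazard ratio would leave the log-rank test in place and gain no power. Use the nominal levels of SAP 5.5.3, which are 0.0054 at the interim and 0.0439 at the final analysis, adjusted for the actual number of deaths. Keep the stratified log-rank test and the unadjusted stratified Cox hazard ratio as supportive. This also settles which test is primary. State that this is the multivariate model foreseen in Protocol XVI, so that the two documents agree.

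The cost is one SAP paragraph and no new data. Three downsides should be stated:
- The adjusted hazard ratio is a conditional effect and will differ from the marginal one used for sizing (0.509 to 0.547 against 0.557 in simulation B).
- SAP 8.1.4 does not replace missing data by default, so patients without a baseline AFP would drop out of the model unless a simple rule is added.
- Simulated type I error was 5.4% with covariates against 5.1% without, a small difference worth confirming for the final specification.
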